#### 11.4 Methods for Evaluation of Measurable Disease

All measurements should be taken and recorded in metric notation. All baseline evaluations should be performed as closely as possible to the beginning of treatment and never more than 6 weeks before the beginning of the treatment.

The same method of assessment and the same technique should be used to characterize each identified and reported lesion at baseline and during follow-up. Imaging-based evaluation is preferred to evaluation by clinical examination when both methods have been used to assess the antitumor effect of a treatment.

Conventional CT, PET/CT (all are optional), and MRI These techniques should be performed with cuts of 10 mm or less in slice thickness contiguously. Spiral CT should be performed using a 5 mm contiguous reconstruction algorithm. This applies to tumors of the chest, abdomen, and pelvis.

#### 11.5 Response Criteria (via RECIST 1.1)

#### 11.5.1 Evaluation of Target Lesions

Complete Response (CR): Disappearance of all targeted and *Non-Targeted* lesions

Objective Response (OR): At least a 30% decrease in the sum of the

longest

diameter (LD) of targeted and *Non-targeted* lesions,

taking as reference the baseline sum LD

Progressive Disease (PD): At least a 20% increase in the sum of the LD of

Targeted or Non- Targeted lesions, taking as reference the smallest sum LD recorded since the treatment started or the appearance of one or more new lesions

Stable Disease (SD): Neither sufficient shrinkage to qualify for PR nor

sufficient

increase to qualify for PD, taking as reference the

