#### 11 MEASUREMENT OF EFFECT

#### 11.1 Antitumor Effect-Solid Tumors

For the purposes of this study, patients should be re-evaluated for response 8 weeks after the initial treatment, 16 weeks after treatment, and at 6 month intervals thereafter.

Response and progression will be evaluated in this study using the new international criteria proposed by the Response Evaluation Criteria in Solid Tumors (RECIST 1.1) Committee (30). Changes in only the largest diameter (unidimensional measurement) of the tumor lesions are used in the RECIST criteria.

The RECIST read at 16 weeks will be used to determine the objective response rate for the primary endpoint of this study.

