#### 11.3 Disease Parameters

Measurable Disease: Measurable lesions are defined as those that can be accurately measured in at least one dimension (longest diameter to be recorded) as  $\geq 0.5$  cm with diagnostic techniques (CT, PET/CT (all are optional), or MRI). All tumor measurements must be recorded in centimeters.

Non-Measurable Disease: All other lesions (or sites of disease), including small lesions (longest diameter <0.5 cm with diagnostic techniques), are considered non-measurable disease. Bone lesions, leptomeningeal disease, ascites, pleural/pericardial effusions, lymphangitis, inflammatory breast disease, and cystic lesions are all non-measurable.

Target Lesions: Target lesion in this study will be considered metastatic sites up to a maximum of 3 lesions per patient. They should be recorded and measured at baseline. Target lesions should be equal to or larger than 1.0 cm in the smallest

cross-sectional diameter on CT or MRI and/or any lesion that shows increase metabolic uptake on PET/CT scans.

Non-Target Lesions: Non-Target lesion in this study will be considered metastatic sites up to a maximum of 10 lesions per patient. They should be recorded and measured at baseline. Non-target lesions should be equal to or larger than 0.5 cm in the smallest cross-sectional diameter on CT or MRI and/or any lesion that shows increase metabolic uptake on PET/CT scans. Importantly, a sum of the longest diameter (LD) for all *non-target* lesions will be calculated and reported as the baseline sum LD. The baseline sum LD of the *non-target* lesions will be used as reference by which to characterize the objective tumor response.

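### Section 11.5.1 counts the targeted lesions in the primary 16-week response, contradicting 11.3, 15.5 and the synopsis, and 11.3 never ties 'target' to irradiation

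*Combined protocol and SAP*

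**What the plan says.** - **Endpoint (11.1).** "The RECIST read at 16 weeks will be used to determine the objective response rate for the primary endpoint of this study". Section 15.2 also places the primary endpoint at 16 weeks.
- **Response criteria (11.5.1).** The 30% fall is taken over the "diameter (LD) of targeted and *Non-targeted* lesions". CR is "Disappearance of all targeted and *Non-Targeted* lesions". PD is a 20% rise in "Targeted or Non- Targeted lesions, taking as reference the smallest sum LD recorded since the treatment started". New disease is listed as a second route to PD: "or the appearance of one or more new lesions". The reference for the 30% fall is the baseline sum LD. The 30% criterion is labelled Objective Response. PR is never defined, although the SD line refers to it and the synopsis states the primary objective as CR+PR.
- **Baseline (11.3).** The baseline sum LD is calculated over non-target lesions, and "The baseline sum LD of the *non-target* lesions will be used as reference by which to characterize the objective tumor response".
- **Primary analysis (15.5).** Response is a 30% fall in the summed diameters of the non-targeted lesions.
- **Best overall response (11.5.2).** Non-targeted lesions again.
- **Synopsis, study design.** Response is read from the non-irradiated lesions.
- **What 'target' means (11.3).** "Target lesion in this study will be considered metastatic sites up to a maximum of 3 lesions per patient"; "Target lesions should be equal to or larger than 1.0 cm in the smallest" diameter, or PET uptake. Non-target lesions number up to 10, at 0.5 cm or more, or with PET uptake. Irradiation is not mentioned.

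**The concern.** The trial asks whether SBRT adds response outside the radiation field, so the primary read has to leave out the lesion that was irradiated. The one section with a full set of CR, response, PD and SD criteria puts the targeted lesions in. If those are the irradiated lesions, the direct local effect of radiation counts toward the primary endpoint, and only SBRT patients can gain from it.

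The split between target and non-target lesions does not settle the matter. A lesion of 1.0 cm or more meets both size criteria in 11.3, and neither depends on irradiation. The reading radiologist and the analyst could each follow the document and score different lesions. If the choice is made after responses are known, the primary result is open to challenge.

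**Working it through.** **1. The sections side by side**

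| Section | Lesions scored | Baseline reference |
|---|---|---|
| 11.5.1 | targeted plus non-targeted | the baseline sum LD, which 11.3 builds from non-target lesions |
| 11.3 | non-target | non-target |
| 15.5 | non-targeted | the baseline sum LD |
| 11.5.2 (best overall response) | non-targeted | not restated |
| Synopsis | non-irradiated | not stated |

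Section 11.5.1 disagrees with the rest on which lesions are scored, and its sum does not match its own reference. With two equal stable lesions, one target and one non-target, the follow-up sum is 2 units against a baseline of 1, a rise of 100% in a patient in whom nothing changed.

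**2. One patient, three answers** (assumed sizes). The irradiated lesion, recorded as target, goes from 4.0 to 1.6 cm. The other, recorded as non-target, stays at 3.0 cm.
- All lesions against an all-lesion baseline: (1.6 + 3.0)/(4.0 + 3.0) - 1 = 4.6/7.0 - 1 = -34%, a response.
- Non-target only (11.3, 15.5): 3.0/3.0 - 1 = 0%, no response.
- 11.5.1 sum over the 11.3 baseline: 4.6/3.0 - 1 = +53%, no response.

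**3. When the irradiated lesion alone is enough** (all-lesion baseline, other lesions stable). If it holds share s of the baseline sum, it must shrink by 0.3/s: 75% at s = 0.4, 60% at 0.5, 50% at 0.6. Below a 30% share it cannot produce a response alone.

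**4. Effect on the primary test, all-lesion baseline.** From the documents: 73 per arm (synopsis), and a one-sided test at 5% (15.2, whose printed 0.05% is read as 0.05). The control rate of 40% is 15.2's figure for single-agent melanoma. Assumed, because the documents do not give them: k lesions of equal size; a patient-level relative change that is normal with SD 0.45; extra shrinkage e of 20% or 40% in the irradiated lesion; no effect outside the field.

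With common size ratio r, the sum in an SBRT patient is r(k - e)/k of baseline, so response requires r ≤ 0.7k/(k - e) instead of r ≤ 0.7. The SBRT response rate is Φ(z + (0.7k/(k - e) - 0.7)/0.45), with z = Φ⁻¹(0.40) = -0.253. For k = 2 and e = 0.2 the threshold is 1.4/1.8 = 0.778 and the rate is Φ(-0.253 + 0.173) = 46.8%. Rejection is by exact enumeration of the pooled z-test; with no distortion it is 5.4%.

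| Lesions k | SBRT response, e = 0.2 / 0.4 | Rejection, e = 0.2 / 0.4 |
|---|---|---|
| 2 | 46.8% / 55.4% | 22% / 62% |
| 3 | 44.3% / 49.4% | 14% / 33% |
| 4 | 43.2% / 46.8% | 11% / 22% |
| 6 | 42.1% / 44.3% | 9% / 14% |
| 8 | 41.5% / 43.2% | 8% / 11% |
| 13 | 40.9% / 41.9% | 7% / 9% |

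Thirteen is the most that 11.3 allows to be recorded (3 + 10). Over SD 0.30-0.60 and control rates of 25%, 40% and 61%, rejection spans 14.5-89% with two lesions, 8.6-37% with four and 6-11% with thirteen.

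**5. What remains if only non-irradiated lesions are scored.** Controls then score k lesions and SBRT patients k - 1. With a share w of 0.25 or 0.50 of the variance lying between lesions within a patient (assumed), and control response fixed at p0, the difference is Φ(Φ⁻¹(p0)·√[(1 - w + w/k)/(1 - w + w/(k - 1))]) - p0. At p0 = 40% and k = 2 this is +0.6 to +1.3 points. Over p0 of 25-61% it is -1.4 to +3.0 points at k = 2, and under 1 point in either direction at k = 4 or more.

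**The case against.** The best counter-argument is that the intent is plain. Section 15.5 is the specific statement for the primary analysis and scores non-targeted lesions. Sections 11.3 and 11.5.2 agree, the synopsis says non-irradiated, and 4.4 uses 'targeted' in the radiation sense. Most of this stands: 11.5.1 is better described as one outlier than as one of several equal rivals. It does not close the gap. No section equates target with irradiated, the definitions in 11.3 point elsewhere, no precedence rule is given, and 11.1 sends the primary endpoint to the RECIST read whose criteria are in 11.5.1.

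A reader might also infer from 11.5.1 taken literally, with its sum divided by the non-target baseline, that response becomes nearly unreachable or that the bias could run against SBRT. The documents do not support presenting that as a likely trial outcome. A rule that scores a stable patient at +100% would be noticed and not used. The mismatch is evidence of a drafting error.

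The rejection rates rest on assumed inputs. The 62% needs two equal lesions and the larger assumed local effect, and the distortion fades as lesions increase. That is correct, and the contradiction does not depend on these figures.

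**Conclusion.** The point holds and should be corrected before responses are read. Section 11.5.1 contradicts 11.3, 15.5 and the synopsis on which lesions decide the primary endpoint, and 11.3 does not tie its lesion classes to irradiation. The reading that does damage is 11.5.1 with an all-lesion baseline, which biases the comparison toward SBRT. Under the assumptions shown, a nominal 5% test rejects 22-62% of the time with two lesions and 7-14% with six to thirteen. If non-target means non-irradiated and 15.5 is followed, local shrinkage is excluded and the remaining difference between arms is small.

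The documents do not show that the sponsor intends the all-lesion reading. The defect is that the text permits it and does not state the intended one.

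**What to change.** 1. In 11.3, state that target means the lesion or lesions selected for SBRT, and that non-target means measurable lesions that are not irradiated.
2. In 11.5.1, base the size criteria of the primary endpoint for CR, the 30% response and PD on non-irradiated lesions only, against a baseline sum over those same lesions. Label the 30% criterion PR. Keep new lesions as progression.
3. Align the synopsis, 11.5.2 and 15.5 with this wording.
4. Report the response of the irradiated lesion separately, as local response.

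Optional: at the step in 5.1.1 where the radiation oncologist states that a lesion can be treated, record before randomisation, in every patient, which lesion that would be. Then report as a sensitivity analysis the response that omits the nominated lesion in both arms. This addresses the small remaining asymmetry and is not needed to repair the definition.

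Cost: wording only for items 1-3 and one extra summary for item 4. The optional step adds one baseline CRF field, and its sensitivity analysis scores one fewer lesion in each control patient.

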#### 11.5.4 Clinical Response Parameters

**Time to Local Progression (TTLP)** is defined as the elapsed time from the start of treatment to the date of documented local progression or death, whichever happens earliest.

**Progression-Free Survival (PFS)** is defined is the time from starting treatment to the time of first documented tumor progression or death due to any cause, whichever occurs first. Death is considered as an event here. For subjects whose disease does not progress or who do not die, PFS will be censored at the time of the last visit.

*Time to Progression (TTP)* is defined as the time from starting treatment to the time of first documented tumor progression. Subjects who do not progress will be censored at the time of the last contact. In addition, death from any cause will also be censored.

Overall Survival (OS) is defined as the time from starting treatment until death due to any cause. For subjects who do not die, time to death will be censored at the time of last contact.

**Locoregional Control (LRC)** is defined as the time from starting treatment until local and/or regional relapse is documented

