#### 12.4 Stereotactic Body Radiation Treatment

It is difficult at this time to predict with confidence the complication rate from the proposed SBRT; however, it is reasonable to extrapolate from the current experience and reported literature with SBRT. One significant toxicity is radiation pneumonitis, which can be manifested as fever, increased excertional dypsnea, pleuritic chest pain, and peritumoral infiltrate on chest imaging. It generally occurs between 1 to 3 months of completion of radiotherapy. The risk of grade 2-4 radiation pneumonitis is aproximately 10-15% in patients treated with standard fractionated large field radiotherapy and higher in patients treated with combined chemoradiotherapy. It is highly dependent on the volume of the lung treated to high dose and the mean lung dose. At this point, the incidence of RT pneumonitis from SBRT combined with immunotherapy for small pulmonary tumors is unknown. However, if the treated tumor volume is kept  $\leq 65$  cc, the risk should be <10-15% with the proposed dose level.

Other toxicities commonly associated with such treatment includes colitis, diarrhea, hypophysitis, rash, arthritis, fatigue, nausea, vomiting, anorexia, and weight loss. Some of these symptoms can also be due to tumor progression. Clinical and radiographic assessments will be performed as indicated to identify all adverse effects, ascertain their etiology, and provide the most appropriate palliative measures. Complications orther than radiation pneumonitis, if any, will be graded according to the Common Toxicity Criteria, National Cancer Institute, version 4.0.

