#### 15.8 Evaluation of Response

All patients included in the study must be assessed for response to treatment, even if there are major protocol treatment deviations or if they are ineligible. Each patient will be assigned one of the following categories: 1) complete response, 2) partial response, 3) stable disease, 4) progressive disease, 5) early death from malignant disease, 6) early death from toxicity, 7) early death because of other cause, or 8) unknown (not assessable, insufficient data).

All of the patients who met the eligibility criteria (with the possible exception of those who received no study medication) should be included in the main analysis of the response rate. Patients in response categories 4-8 should be considered to have a treatment failure (disease progression).

All conclusions should be based on all eligible patients. Sub-analyses may then be performed on the basis of a subset of patients, excluding those for whom major protocol deviations have been identified (e.g., early death due to other reasons, early discontinuation of treatment, major protocol violations, etc.). However, these sub-analyses may not serve as the basis for drawing conclusions concerning treatment efficacy, and the reasons for excluding patients from the analysis should be clearly reported. The reason for performing subset analyses would be to generate hypotheses for future prospective clinical trials.

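### Progression counts the irradiated lesion with no rule for radiation change, and the week-8 CT falls in the plan's own infiltrate period; PFS needs a sensitivity analysis that sets that lesion aside in both arms

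*Combined protocol and SAP*

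**What the plan says.** **Response.** The synopsis takes response from the non-irradiated lesions. Sections 11.3, 11.5.2 and 15.5 use the Non-Targeted lesions. Section 11.5.1 is not aligned with these, since its response definition adds the targeted lesions. Section 11.1 makes the 16-week read the primary endpoint.

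**Progression.** Section 11.5.1 sets the threshold at a rise of 20% or more in summed longest diameter. It names the lesions and the reference value as "Targeted or Non- Targeted lesions, taking as reference the smallest sum LD recorded since the treatment started". The second trigger in that section reads "or the appearance of one or more new lesions". Both lesion classes count. No section exempts an irradiated lesion, asks for confirmation of progression, or says how change inside the treated field is read.

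**Target lesions.** Section 11.3 says "Target lesion in this study will be considered metastatic sites up to a maximum of 3 lesions per patient". It does not say that a target lesion is the irradiated one.

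**Radiation change.** Section 12.4 says radiation pneumonitis can show as "peritumoral infiltrate on chest imaging. It generally occurs between 1 to 3 months of completion of radiotherapy".

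**Use of progression.** PFS in 11.5.4 runs to "first documented tumor progression or death due to any cause, whichever occurs first". Section 11.5.2 closes the best-response period at progression, and 15.8 treats a patient categorised as progressive disease as a treatment failure. Section 11.5.5 gives review of responses to a co-investigator radiologist, with no rule for radiation change and no mention of blinding to arm.

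**The concern.** The plan protects response from direct effects of radiation by looking away from the treated lesion, but gives progression no such protection. Only one arm receives protocol radiation, and the first on-treatment scan includes the treated site at a time when the plan itself expects infiltrate there. A reader who measures infiltrate as part of the lesion, or calls it a new lesion, would record progression that reflects treatment change rather than tumour.

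PFS, time to progression, local progression, duration of response and stable disease of at least six months all depend on that call. PFS and stable disease are named secondary objectives. A second question is whether a patient with week-8 progression confined to the treated field can still be a week-16 responder on the Non-Targeted lesions. Sections 11.5.2 and 15.8 do not settle it.

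**Working it through.** The plan gives no event count, hazard ratio or power for PFS, so there is no planned figure to reproduce. The 146-patient sample size concerns the 16-week response and plays no part here.

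**1. Timing.** Inputs: SBRT on days 1-21 of CBI cycle 1 (6.2); CT including the treated site at weeks 8 and 16, each ±10 days (6.3); infiltrate at 1-3 months, about days 30-91 (12.4). All fractions are taken to fall within days 1-21.
- Week 8, nominal: 56 − 21 = 35 to 56 − 1 = 55 days after SBRT.
- Week 8, with window: 56 − 10 − 21 = 25 to 56 + 10 − 1 = 65 days.
- Week 16, nominal: 112 − 21 = 91 to 112 − 1 = 111 days; with window 81 to 121.

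The whole nominal week-8 range lies inside days 30-91. Week 16 lies at or beyond its end.

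**2. Does the irradiated lesion count?** Section 11.3 does not equate target with irradiated, but 11.5.1 counts both classes, so a recorded irradiated lesion counts under either label.

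**3. How much growth is needed?** For 20 mm lesions: one in the sum needs 0.20 × 20 = 4 mm; two pooled need 0.20 × 40 = 8 mm; three need 0.20 × 60 = 12 mm. Shrinkage elsewhere in the sum raises the requirement. The plan does not say whether target and non-target sums are pooled for progression.

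**4. Can the size be derived?** The share f of the SBRT arm wrongly scored at week 8 is (share with a lung lesion irradiated) × (share of those with infiltrate scored as progression). The first factor is not given. For the second, 12.4 gives 10-15% as the grade 2-4 pneumonitis rate for large-field conventional radiotherapy, calls the rate for SBRT with immunotherapy unknown, and says only that for small treated volumes "the risk should be <10-15% with the proposed dose level". So f cannot be computed.

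**5. What-if, with f assumed.** Simulation with 73 per arm, 300 runs per setting, exponential PFS with control median 4 or 8 months, progression seen at days 56, 112, 182, 365, 547 and 730, and false progression placed at week 8 in the SBRT arm. No local-control benefit is modelled.

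| Assumed f | True HR 1.0 reads (median 4 / 8 mo) | True HR 0.70 reads (median 4 / 8 mo) |
|---|---|---|
| 0% | 0.992 / 0.992 | 0.707 / 0.694 |
| 2.5% | 1.020 / 1.019 | 0.738 / 0.724 |
| 5% | 1.047 / 1.046 | 0.745 / 0.751 |
| 10% | 1.090 / 1.122 | 0.793 / 0.825 |

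The SBRT-arm share progression-free past six months falls by 1.0 point (0.356 to 0.346) at the least and 7.8 points (0.701 to 0.623) at the most. If the 10-15% reference rate applied and every case were scored as progression, f = 2.5% would need a lung share of 17-25% (0.025/0.15 to 0.025/0.10), and f = 10% would need 67-100%. The 10% row is therefore an extreme. The table shows sensitivity and does not estimate the bias.

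**The case against.** The strongest case against has four parts.

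- **The text does not make infiltrate progression.** Section 11.5.1 speaks of new lesions, 11.5.4 of tumour progression, and 12.4 treats infiltrate as a sign of toxicity. A radiologist reviews responses, and RECIST 1.1 is invoked by reference. A reader might infer that any new opacity is progression as written; the documents do not say so. What stands is that they do not say the opposite either, and the radiologist is given no rule.
- **The direction is not one-way.** A reader might infer that the artefact can only hurt SBRT. But counting the irradiated lesion also credits SBRT with local control: section 4.2 cites control rates above 75%, while a comparable control-arm lesion can grow and count as progression. CBI can itself cause pneumonitis in either arm (4.2, 7.2.2.2). This stands, and the net direction is unknown.
- **The frequency may be low.** The infiltrate text concerns lung targets only. If onset were uniform over days 30-91 (an assumption), only (35 − 30)/61 = 8% to (55 − 30)/61 = 41% of cases would have begun by the nominal week-8 scan. Infiltrate without symptoms would add to a grade 2-4 rate, but no figure is given. This stands against quoting a patient count.
- **Requiring confirmation in the SBRT arm alone would bias the comparison.** Growth that then stabilised would never count there but would count at once in controls. After week 16 the next scan is at six months (6.3, if counted from cycle 1 day 1) or twelve (the section 10 calendar leaves six-month imaging blank), roughly 2-8 months later. This stands, so no such rule is recommended.

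**Conclusion.** The gap is real. Progression includes the irradiated lesion and any new lesion, no rule covers radiation change, and the nominal week-8 CT falls wholly within the plan's own infiltrate period. In-field change in irradiated lung lesions could therefore be scored as progression in the SBRT arm.

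The exposure is on secondary measures. Section 15.6 plans estimates, intervals and medians with no stated test, so no planned power is lost. Neither the net direction nor the size can be derived, because the share of lung targets and the pneumonitis rate for SBRT plus CBI are not given.

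A reader might go further and subtract percentage points from the planned gain in response. The documents do not support that. The primary endpoint is the week-16 read, defined in 15.5 on Non-Targeted lesions, and it is affected only if earlier in-field progression outranks a Non-Targeted response. Sections 11.5.2 and 15.8 leave that open, which is reason to settle it in the text rather than to assume a loss.

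**What to change.** 1. At enrolment, before randomisation, record in both arms the lesion judged treatable with SBRT under inclusion criterion 5.1.1.
2. Add a sensitivity analysis of PFS, and of stable disease of six months or more, in which progression is based on all other lesions and on new lesions outside that lesion's site, applied alike in both arms. Criterion 5.1.2 ensures that every patient has at least one measurable lesion left to follow.
3. State in 11.5.1 and 15.8 that, for the primary endpoint, progression confined to the irradiated lesion or its field does not override the week-16 response of the Non-Targeted lesions.

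These are analysis rules and leave clinical decisions as they are. The cost is wording, one baseline data field and one extra analysis, with no added scans. The sensitivity analysis ignores true progression in the designated lesion in both arms, so all-lesion PFS should remain the main secondary analysis. It cannot help the local-progression measures, which depend on the treated field itself.
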